5.5.3. Replacements

Participants that withdraw consent from the study during the Run-in period (i.e., before randomization) or do not qualify for study continuation at the end of the Run-in period will be replaced until the target number of randomized study participants is reached. Participants that withdraw consent from the study or discontinue the study drug after randomization will not be replaced.

5.5.4. Termination of Study

Premature termination of this clinical trial may occur because of a regulatory authority decision, drug safety problems as determined by the Data Safety Monitoring Board (DSMB), or at the discretion of the funding agency (NIDDK).

6. STUDY TREATMENTS

6.1. Study Drug Description, Dosage, Administration, and Accountability

6.1.1. Description

Eligible study subjects who agree to participate in the study will all be randomized to receive placebo or allopurinol – a serum UA lowering medication that has been on the market since 1964 as the main drug for the therapy of symptomatic hyperuricemia and for the prophylaxis of gout in cancer patients receiving chemotherapy. Allopurinol is an inhibitor of xanthine oxidase, which is responsible for the conversion of hypoxanthine to xanthine and of xanthine to UA. It is metabolized to the corresponding xanthine analogue, oxypurinol (alloxanthine), which is also an inhibitor of xanthine oxidase. At the average dosage (300 mg/day), allopurinol causes a 30-40% reduction in serum UA²⁴⁻²⁶, but up to a 60% reduction can be obtained using the maximum dosage of 600 mg.²⁷ While allopurinol is mostly used in individuals with gout and very high UA levels, several studies have shown that it is also effective at lower UA levels²⁷⁻²⁹.

Because of its rapid oxidation to its active metabolite oxypurinol, allopurinol has a short plasma half-life (~1-2 hrs). However, since oxypurinol has a longer half-life (~15 hrs), effective xanthine oxidase inhibition can be maintained over 24 hrs with a single daily dose of allopurinol. Since both allopurinol and oxypurinol are eliminated through the kidneys, patients with impaired renal function require lower doses than those with normal renal function. A common rule of thumb is to use 75% of the dosage in individuals with eGFR in the 50-90 ml/min range, and 50% of the dosage in individuals in the 10-50 ml/min range.

6.1.2. Dosage

After an initial four weeks where all participants randomized to allopurinol will take 100 mg per day, the allopurinol dosage will vary from 200 to 400 mg per day based on eGFR levels. Participants will take 400 mg per day if their eGFR is ≥ 50 ml/min/1.73 m², 300 mg per day if their eGFR is in the 25 to <50 ml/min/1.73 m² range, and 200 mg per day if the eGFR is in the 15 to <25 ml/min/1.73 m² range. Allopurinol will be continued at this dosage throughout the study unless the eGFR changes, in which case the dosage will be modified to that appropriate for the new eGFR class.

All participants, whether they are randomized to allopurinol or placebo, will be given four tablets per day to be taken orally following breakfast. Tablets will be provided in four vials (A, B, C, and D) or in blister packs, in which each blister contains the four tablets for a given day. If the medication is provided in bottles, participants randomized to allopurinol will receive a dosage of 100 mg as a 100 mg tablet (from vial A) plus three placebo tablets (from vials B, C, D), 200 mg as two 100 mg (from vials A and C) and two placebo tablets (from vials B and D), 300 mg as three 100 mg (from vials A, B, C) and one placebo tablet (from vial D), 400 mg as four 100 mg tablets (from vials A, B, C, D). Subjects randomized to placebo will be given four placebo tablets (from vials A, B, C, D). If the medication is provided in blister packs, each blister will contain the four tablets for a given day, with the same proportion of active and placebo tablets described above for each allopurinol dosage and for placebo.

The dose adjustment will be carried out as follows:

1. At each follow-up visit, a study drug requisition will be sent by the clinical site to the research pharmacy indicating the study ID, name, and address of the participant, the most recent eGFR value (CKD-EPI), calculated using a recent local lab creatinine value, and the number of days to be covered by the drug supply.
2. At the pharmacy, a clinical pharmacist will determine the allopurinol dose (ranging from 0 to 400 mg) that should be given at that time according to the study protocol given the participant's treatment assignment and the most recent eGFR value (CKD-EPI) calculated using a recent local lab serum creatinine value.
3. The research pharmacy will mail the new batch of study medication directly to the study participant.
4. At some sites the study medication may be dispensed directly to the study participant at a relevant in person study visit or by mail from the site following a relevant in-person or phone study visit.
5. Participants will be instructed to immediately inform the clinical site upon receipt of the new tablets and mail the pill bottles or blister packs with the tablets remaining from the previous prescription in a provided pre-addressed mailer, to the clinical site for drug accounting and compliance assessment.

6.1.3. Compliance and accountability

Skills will be taught and reinforced at each visit with regard to scheduling and administration of pills at home and while traveling. Methods (e.g. record-keeping) will be taught to help participants monitor tablet usage and enhance compliance. To complement the regular compliance interventions at the scheduled visits, study information and motivational materials (postcards, newsletters, etc.) will be mailed. In addition, at midpoint between clinic visits, participants will be phoned by the clinic staff to review pill-taking. Patients will be provided with random but known numbers of excess medications, providing extras in case of pill loss. Adherence will be monitored by instructing participants to expect extra pills and to mail the pill bottles or the blister packs with the tablets remaining from the previous prescription to the study center upon receipt of a new batch of tablets. The number of extra pills included in each supply of medications will be decided by the pharmacist, who will keep a record of it and will transmit this information to the Study Site. Personnel at the Study Site will enter this

information in the appropriate electronic Case Report Form along with the expected number of pills used during the period covered by the supply and the number of unused pills returned by the participant. These data will be used to analyze compliance. If poor adherence is noticed, measures will be taken to increase compliance, such as explaining the purpose of the study again, providing pill reminders, and more frequently contacting the study subject by phone. Participants at each visit will be asked about their perceived compliance and about any difficulties with taking the study medications, but the individualized strategies to improve compliance will not be openly linked to the pill counts, i.e. participants will not be informed of the results of pill counting. Participants showing poor compliance will not be withdrawn from the study.

6.2. Blinding Procedures

Study participants, the investigators and research staff at the Clinical Sites, and the PERL co-PIs (Drs. [name] and [name]) will be blinded to treatment assignment whereas the Data Coordinating Center Co-Directors and staff and the pharmacy personnel will have access to this information. Serum uric acid values, from which the treatment assignment might be inferred, will not be transmitted to the Clinical Sites by the central or local laboratory and will not be available for viewing in the study database. Should unblinding of a study participant be necessary because of an emergency, the site personnel will login to the password-protected electronic database application that will provide the treatment assignment. Audit procedures will ensure that the name of the individual associated with the login will be communicated to the Data Coordinating Center project manager and Co-Directors. As an additional safety measure, the personnel at the Clinical Sites will be provided with telephone numbers to contact the Data Coordinating Center and/or Pharmacy personnel having access to the treatment assignment on a 24-7 basis. If unblinding occurs, the circumstances that led to it will be reviewed and reported.

7. STUDY OUTCOMES

7.1. Primary outcome

The primary outcome will be the iGFR at the end of the 2-month wash-out period following the 3-year treatment period, measured by the plasma clearance of non-radioactive iohexol (iGFR) and adjusted for the iGFR at baseline. The rationale of measuring the primary outcome at the end of the wash-out period is to test allopurinol for permanent effects of on the natural history of kidney disease, independent from any transient, hemodynamic effect that the medication may have on GFR. Plasma iohexol clearance has been shown to provide accurate and reproducible GFR measurements.^{30,31} It is highly correlated with inulin clearance (the gold standard to measuring GFR)³² and is a safe, cost-effective method to test hundreds of patients enrolled in multicenter clinical trials.³³ The method consists of injecting a 5 mL bolus of Iohexol (Omnipaque, 300 mg iodine/mL) and drawing blood samples at baseline and 120, 150, 180, 210, and 240 minutes after the injection. Plasma concentrations of iohexol at different time points are measured by HPLC and used to calculate the plasma clearance of iohexol ($Cl = \text{Dose}/\text{AUC}$, where AUC is the area under the plasma concentration time curve), which is taken after appropriate body surface area corrections as a measure of GFR.^{30,31}

7.1.1. iGFR quality assurance

It is of the foremost importance that reliable iGFR measurements are obtained. To maximize accuracy and precision, the following procedure will be in place.

1. Personnel performing the iohexol clearance test will undergo a standardized training program administered under the Site Directors' supervision through in-person meetings or on-line modules. All clinical site staff will complete the online knowledge testing in order to perform the tests.
2. Participants will be instructed to discontinue non-steroidal anti-inflammatory drugs (NSAIDs) for at least 3 days and avoid large protein meals for one day prior to the test, since these

could influence GFR. They will also be instructed to aim for a fasting glycemia between 90 and 160 mg/dl on the day of the test. Before the test, participants will have a light breakfast at the clinic along with their morning insulin. The insulin dose will be adjusted to keep their blood glucose in the 90-160 mg/dl range. If blood glucose is outside this range right before or during the test, small amounts of intravenous insulin (if blood glucose is too high) or orange juice/milk (if glucose is too low) may be administered to bring blood glucose levels within the desired interval.

3. In the case of extreme deviations from the target blood glucose values, the test may be rescheduled to another day (within 2 weeks). The test will also be postponed in the case of recent febrile illness, diarrhea or vomiting, dehydration, poor fluid intake, recent intake of nephrotoxic drugs such as NSAIDs, urinary tract infection, or a positive pregnancy test.

7.1.2. iGFR quality control

The quality of iGFR results will be monitored by:

1. Systematically checking for deviations from the study protocol, such as deviations from the target blood draws time points during the test or the presence of medical conditions that should have prompted a postponement of the test.
2. Calculating the R-square (R^2) of the regression between log-iohexol values and time. iGFR tests will be defined as technically acceptable if the R^2 is >0.90 . R^2 calculations will be performed by the DCC using all 5 time points of the iGFR test.

7.1.3. Technically unacceptable iGFR measures

If an iGFR test is deemed to be technically unacceptable according to the above QC criterion ($R^2 \leq 0.90$), or a study protocol deviation is suspected, the following procedures will be followed:

1. Source documents related to the test in question will be reviewed to verify whether there was a protocol deviation or a technical error in the iGFR procedure (e.g., presence of contraindications to iGFR, swapping of tubes, wrong collection times, typos, etc.). In the case of an $R^2 \leq 0.90$, the iohexol measurements will be repeated by the central laboratory.
2. If a technical error is found and the error can be rectified, or the new laboratory measures yield an $R^2 > 0.90$, the iGFR value will be recalculated after the appropriate corrections are made. The study site or the central laboratory, as applicable, will be alerted about the error and measures aimed at improving iGFR quality will be implemented.
3. If the error is confirmed and cannot be fixed, or no error can be found, the iGFR will be dropped and will be repeated within 4 weeks from when the iGFR results become available.
4. If the repeated test is technically unacceptable, or the test cannot be repeated within 4 weeks for logistical reasons, the iGFR value at that time point will be considered as missing for the analysis of the primary outcome. It is therefore critical that every effort be made to obtain this repeat iGFR measure.

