- j. Most of the participants will already be on RAS Blockers. For those who were not previously taking these medications, risks will be minimized by not prescribing RAS Blockers to participants who have contraindications to these drugs and by prescribing an ARB whenever ACE inhibitors are contraindicated. If adverse events develop that are deemed to be related to the use of RAS blockers, the dose of these drugs will be decreased, followed by their discontinuation if the problem persists (see 8.2. Run-in period), thus adhering to current standards of care. If receiving discontinuation of RAS blockade becomes necessary, BP will be managed by alternate drugs as described above.
- k. Blood pressure will be measured quarterly with the goal of maintaining BP ≤ 140 mmHg systolic and ≤ 90 mmHg diastolic. If elevated, a recheck will be performed within 2 weeks and if still elevated additional antihypertensive non-RAS blockers will be added in collaboration with the participants' physicians. Failure to achieve satisfactory BP control within 2 months would lead to a case review by the Drug Monitoring Committee.
- l. Participants with a decrease in both iGFR (meeting the R^2 criterion described in 7.1.2) and eGFR from one measurement to the following one corresponding to a GFR decline $> 20\%$ per year will be referred to a nephrologist to investigate the causes of such rapid loss of kidney function. If a decrease of such magnitude is observed for the iGFR but is less than a 20%

decline per year for the eGFR, the iGFR measurement will be repeated. If the >20% per year iGFR decrease is confirmed, the participant will be referred to a nephrologist for further evaluation. In this case, the first iGFR value will be used for the analysis of the primary outcome. If the >20% per year iGFR decrease is not confirmed, the participant will not be referred to a nephrologist. The first iGFR test will be reviewed to verify whether medical conditions that should have prompted a test postponement, such as dehydration or recent use of NSAID (see 7.1.1.3), were present. In that case, the repeated iGFR value will be used for the primary outcome analysis. Otherwise, the first iGFR value will be used.

- m. Data monitoring will be performed on a regular basis. Data entry computers will be programmed to flag any parameters outside clinically acceptable ranges.

c. Protection of confidentiality

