6.3. Visit windows

To provide scheduling flexibility to study sites and participants, visits were required to occur within a protocol-defined window rather than on a specific date. The protocol-defined visit windows are summarized in the tables 6.3.1 and 6.3.2 below. For analytic purposes, the visit windows defined in the protocol will be expanded in order to eliminate gaps between them. This will ensure that all observations, including those that may have occurred outside a protocol-specified time window, will be associated with the most appropriate visit and therefore properly included in the analysis. If multiple observations occur within a window, the one closest to the visit target date will be utilized. If two observations are equi-distant from the target date, the first one will be utilized.

As iGFR is the primary and key secondary endpoint, the protocol allowed for repeats of the iGFR procedure in order to achieve qualified iGFR values. Also, the procedure required a longer visit, so it was more difficult to schedule. Thus, we allowed wider windows for iGFR visits (V11, V16 and V17) to ensure that all qualified iGFRs are analyzed. In addition to avoid over-writing iGFR visits with a non-iGFR (V6-V10, V12-V15) visit, and vice-versa the aforementioned procedure will be performed separately for non-iGFR (Table 6.3.1) and iGFR visits (Table 6.3.2).

Table 6.3.1. PERL windows for post-randomization non-IGFR visits.

Visit	Lower Boundary of Window (Week, Excluding First day)	Per protocol Target Date window in weeks	Upper Boundary of Window (Week, Including last day)	Time since randomization attributed to visit window (in weeks)
Visit Windows relative to Randomization Date				
Visit 6	0	4 [3-5]	10	5
Visit 7	10	16 [14-20]	24	17
Visit 8	24	32 [30-34]	40	32
Visit 9	40	48 [46-50]	56	48
Visit 10	56	64 [62-66]	72	64
Visit 12	88	96 [94-98]	104	96
Visit 13	104	112 [110 -114]	120	112
Visit 14	120	128 [126 -130]	135	128
Visit 15	135	142 [140 -146]	150	142

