We will also include eGFR at all post-randomization visits, i.e., Visit 6-17, iGFR at Visits 11, 16 and 17, AER at Visits 15, 16 and 17 expressed on logarithmic base to 10 scale. Imputation of baseline variables will be performed starting with variables having the lowest number of missing values. Variables measured longitudinally, i.e., eGFR and iGFR, will also be modeled sequentially in order determined by visit number. To preserve different response patterns in the study treatment groups (i.e., treatment group by study visit interaction) imputations will be performed separately in each group. Resulting data will consist of 25 imputed datasets. We note that the FCS method imputes data under the missing at random (MAR) assumption, e.g., the probability that the iGFR/eGFR value is missing depends on *observed* rather than *unobserved* values of the variable. Although we consider the MAR assumption to be sensible for our study, it does not apply for post-ESRD iGFR/eGFR values. To model *post-ESRD eGFR* measures as a deviation from the MAR assumption, we will impute these values using a controlled imputation technique, specifically the delta-adjustment approach (O’Kelly, Ratitch, 2014). This technique will impute post-ESRD eGFR values on average at 7 ml/min/1.73m², with a small variation around it, that is consistent with: (1) attributing to missing post-ESRD eGFR values the value representing ‘the worst case scenario’, (2) assigning a biologically acceptable value, and (3) including the ‘absorbing state’ feature of ESRD. We note that eGFR measures are taken at every visit and are used to determine time of developing ESRD. For this reason pre-ESRD eGFR values are highly predictive of post-ESRD iGFR values. In addition, we note that post-ESRD iGFR and eGFR values lie in a very narrow range and they are effectively interchangeable. For these reasons, we will impute post-ESRD iGFR values by using corresponding post-ESRD eGFR imputed values as a proxy. We note that the imputation of *eGFR* and *iGFR* values for subjects who *did not develop* ESRD and have low values to start with may lead to imputed values lower than 15 ml/min/1.73m², which is biologically implausible. For this reason, imputed values of *eGFR* and *iGFR* for subjects who *did not develop* ESRD will be truncated at 15 ml/min/1.73m². Similarly, log(AER) base 10 imputed values for these subjects will be truncated at a lower limit of detection of -0.60206 (= log₁₀(0.25)).

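### As worded, Protocol 7.1.3 has no branch that keeps an iGFR test with R² above 0.90 once it has been queried for a suspected deviation and cleared by review

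*Protocol*

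**What the plan says.** Protocol 7.1.2 sets the acceptance criterion: "iGFR tests will be defined as technically acceptable if the" R² of the regression of log-iohexol on time exceeds 0.90, using all five time points. It also calls for a systematic check for deviations, such as wrong draw times or a medical condition that should have postponed the test.

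Protocol 7.1.3 opens its procedure when R² is 0.90 or less, "or a study protocol deviation is suspected, the following procedures will be followed". The steps are:

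1. Source documents are reviewed. Only where R² is 0.90 or less, "the iohexol measurements will be repeated by the central laboratory".
2. The value is recalculated if an error is found and can be put right, or if the new assay gives R² above 0.90.
3. "If the error is confirmed and cannot be fixed, or no error can be found, the iGFR will be dropped" and repeated within 4 weeks of the results becoming available.
4. If the repeat is unacceptable or cannot be done in that time, "the iGFR value at that time point will be considered as missing for the analysis of the primary outcome".

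SAP 6.5 imputes missing iGFR: "Resulting data will consist of 25 imputed datasets". SAP 6.3 says that "the protocol allowed for repeats of the iGFR procedure in order to achieve qualified iGFR values", but the SAP does not define a qualified value.

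Protocol 13.5.b.7.l covers an iGFR fall of more than 20% per year that eGFR does not match. The test is repeated. If the fall is not confirmed, the first test is reviewed for conditions that should have postponed it. If one was present, the repeat is analysed. "Otherwise, the first iGFR value will be used".

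**The concern.** Dropping a test when no error can be found is reasonable for a poor R² that nobody can explain. On the other route, the same words reach a test that met the acceptance criterion, was questioned, and was found sound. An unfounded suspicion then has the same result as a confirmed error that cannot be fixed.

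The values concerned include the primary endpoint at Visit 17. A valid measurement would be replaced by a later one or, failing that, by an imputed one. The participant would also have another iohexol injection with sampling to 240 minutes. At Visit 4 the stake differs: under Protocol 8.4, a participant for whom no valid iGFR can be obtained is not randomized.

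**Working it through.** **1. Branches of 7.1.3 as worded**

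| First R² | Source review | Re-assay | Outcome |
|---|---|---|---|
| > 0.90, deviation suspected | error found and rectified | not ordered | recalculated and kept (step 2) |
| > 0.90, deviation suspected | error confirmed, cannot be fixed | not ordered | dropped and repeated (step 3) |
| > 0.90, deviation suspected | nothing found | not ordered | dropped and repeated (step 3) |
| ≤ 0.90 | error rectified, or re-assay R² > 0.90 | done | recalculated and kept (step 2) |
| ≤ 0.90 | not fixable, or nothing found | R² stays ≤ 0.90 | dropped and repeated (step 3) |

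The third row is the problem. Re-assay is the only exit that does not depend on finding an error, and it is closed when R² is above 0.90. SAP 6.3 does not reopen it: its rule of taking the observation closest to the target date does not say whether a dropped original still competes with its repeat.

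**2. Number of values**

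The documents give no query rate or repeat rate. Assumed: 2% to 5% of Visit 17 tests are queried and cleared, and 25% to 50% of those are not successfully repeated in time.

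- Tests expected: 530 (SAP 1) × (1 − 0.15) (planned dropout, Protocol 11.10) = 450.5, about 450.
- Dropped: 450.5 × 0.02 = 9.0, and 450.5 × 0.05 = 22.5. That is about 9 to 23.
- Imputed: 9.0 × 0.25 = 2.3, and 22.5 × 0.50 = 11.3. That is about 2 to 11.

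**3. Precision**

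The missing share m runs from 0.02 × 0.25 = 0.5% to 0.05 × 0.50 = 2.5%. Suppose the residual correlation between Visits 16 and 17 is ρ = 0.8. This is an assumption, since Protocol 11.10 says that no covariance matrix was available. The variance inflation is about 1/[1 − m(1 − ρ²)]:

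- m = 0.5%: 1/(1 − 0.005 × 0.36) = 1.002.
- m = 2.5%: 1/(1 − 0.025 × 0.36) = 1.009.

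If imputation recovered nothing, the upper case would be 1/(1 − 0.025) = 1.026 in variance, or about 1.3% in standard error.

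**4. Power, as an outer bound**

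The plan's own figures come first. With effect 3, SD 10.1, two-sided alpha 0.05 and 80% power, n = 2 × (1.960 + 0.842)² × 10.1² / 3² = 178 per group, against the stated 180. Model M1 with 240 × 0.85 = 204 per arm and effect 3 × 0.94 = 2.82 gives power 0.805, against the stated .80. The other five M1 entries in Table 1 also reproduce.

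Now remove a further share of Visit 17 values, with no repeat and no recovery by imputation:

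| Extra share lost | 240 per arm | 265 per arm (530/2) |
|---|---|---|
| 0% | 0.805 | 0.842 |
| 1% | 0.801 | 0.838 |
| 2% | 0.797 | 0.835 |
| 5% | 0.785 | 0.823 |
| 10% | 0.763 | 0.803 |

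The 2.5% upper case in step 3 lies between the 2% and 5% rows.

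**The case against.** The section is headed as dealing with technically unacceptable measures, and a test with R² above 0.90 is acceptable by the protocol's own definition. Step 1 distinguishes a protocol deviation from a technical error, while steps 2 and 3 speak only of an error. The no-error phrase comes straight after the re-assay, which is done only for a low R². On that reading it was meant for an unexplained low R², and the fate of a cleared suspicion is simply not stated. This stands as evidence of intent, and it is why the point should not be read as a deliberate decision to discard good tests. It does not remove the need for a change: on one reading the rule drops a valid value, on the other it gives no outcome.

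A reader might also infer that surprising results are selectively re-tested and the treatment effect biased. The documents do not support that. Protocol 7.1.2 describes systematic checking for deviations, and nothing lets an unexpected value count as a suspected deviation. Site staff and the co-principal investigators are blinded. Data coordinating center staff have access to assignment (Protocol 6.2), and the criteria for suspicion are not set out, so bias cannot be excluded. But no difference between arms and no direction is shown.

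Nor is 13.5.b.7.l a direct contradiction. It is a safety rule with a different trigger, and its review chooses between two measured values after the repeat has been done. It shows the protocol keeping a first value after a clean review, which supports clarifying 7.1.3 and no more.

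Finally, most dropped tests may be repeated. Protocol 7.1.3 asks for every effort to do so, SAP Table 6.3.2 accepts Visit 17 iGFR up to 20 weeks after Visit 16, and the imputation model uses earlier iGFR and serial eGFR. All of this limits the loss.

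**Conclusion.** The point holds as a fault of wording, probably unintended. Followed literally, 7.1.3 drops and repeats a test with R² above 0.90 that review has cleared, and the value becomes missing only if the repeat fails or is not done in time. Nothing in the SAP corrects this.

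The likely size is small. The 9 to 23 dropped and 2 to 11 imputed values rest wholly on the assumed query and repeat rates; actual counts should replace them. Using all 530 randomized as the base would overstate both, since it ignores the planned 15% dropout. The precision loss of about 1% or less also depends on the assumed correlation of 0.8. The sample size calculation is not in question.

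The case for changing the text is that it costs almost nothing and avoids discarding valid primary-outcome measurements and repeating iohexol tests without cause.

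**What to change.** In Protocol 7.1.3, step 3, limit the no-error branch to tests whose R² remains 0.90 or less after re-assay. Add that a test with R² above 0.90 for which review confirms no deviation or error keeps its original value for the analysis and needs no repeat under 7.1.3. The handling of confirmed errors that cannot be fixed stays as it is.

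State that repeats called for by 13.5.b.7.l are unaffected. A bare instruction not to repeat would collide with that section. Reconcile the two sections on which value is analysed when both apply to the same test. In SAP 6.3, define a qualified iGFR in the same terms, so that the choice among observations within a window follows the protocol rule.

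The cost is a sentence or two in the protocol and a definition in the SAP. No further data are needed, and some repeat tests would be saved.
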